#### **Biomarkers, imaging and pharmacokinetics:**

- Serum and urinary biomarkers (CTX-I, PINP, BSAP and TRAP5b in serum and NTX-I, CTX-I,  $\alpha$ CTX-I, and CTX-II in urine).
- Compound index of MRI bone area and cartilage volume
- Pharmacokinetics: MIV-711 PK parameters and their relationship to covariates such as age, weight, gender, liver function and concomitant medications.

##### *7.4.1.1 Biomarkers and biobanking*

Blood and urine samples will be taken at Visits 2, 4, 5 and 6, for analysis of exploratory bone and cartilage markers of relevance for OA disease, such as CTX-I, PINP, BSAP and TRAP5b in serum and NTX-I, CTX-I,  $\alpha$ CTX-I and CTX-II in urine.

A blood and urine sample from Visit 5 will be collected and stored in a biobank according to local biobanking regulations and under a separate voluntary ICF, to enable further profiling (pharmacogenomics, proteomics, genomics, metabolomics and lipidomics). In addition, potential susceptibility genes and genes related to underlying disease may be explored using the same samples. Aliquots of each sample will be retained for up to 5 years by the sponsor or its subcontractor for biobank storage, in line with GCP/Good laboratory practice and biobanking policies. Biological samples used for possible exploratory analysis may be retained at Medivir, Huddinge, Sweden, or at an affiliated storage location detailed in the Laboratory Manual, for a maximum of 5 years following the finalisation of the Clinical Study Report. The results from such analysis will be reported separately from the Clinical Study Report.

##### *7.4.1.2 Imaging*

Change from Visit 8 in Study MIV-711-201 to Visit 5 in the current study in a calculated compound index of MRI bone area (key secondary endpoint) and cartilage thickness.

##### *7.4.1.3 Pharmacokinetics*

The pharmacokinetics and potential metabolites of MIV-711 and their relationship to patient factors and concomitant medications will be analysed following the sampling procedures as described in Section 7.10.

#### **7.4.2 Exploratory Endpoints (Study Population B)**

All secondary and exploratory endpoints described in Section 7.2 and Section 7.4.1, respectively, for Study Population A will be assessed as exploratory endpoints for Study Population B and will be evaluated over 26 weeks.

## 7.5 Physical Examination

A standard complete physical examination will be performed at Visit 1 (Screening), Visit 2 (Enrolment), Visit 3, Visit 4 and Visit 5. The following parameters and body systems will be examined and any abnormalities will be described: general appearance, skin (presence of rash), head, eye, ears, nose, and throat, lungs (auscultation), heart (auscultation for presence of murmurs, gallops, rubs), extremities exam for the presence of peripheral oedema, abdominal (palpation and auscultation), neurologic (mental status, station, gait, reflexes, motor and sensory function, coordination) and lymph nodes.

A standard clinical examination of both knees will be undertaken at all visits. Any clinically significant changes from Visit 2 (Enrolment) should be recorded as AEs.

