## 7 ENDPOINT AND METHODS OF ASSESSMENT

### 7.1 Primary Endpoint (Study Population A)

The primary objective is to study the safety and tolerability of MIV-711 in OA patients who have received treatment for up to 52 (26+26) weeks.

Safety endpoints:

- Incidence and severity of AEs
- Incidence and severity of clinical laboratory abnormalities
- Physical examination findings by patient
- Incidence and severity of ECG abnormalities
- Mean change from Baseline (Visit 2 of Study MIV-711-201) in vital signs (blood pressure, heart rate, temperature) and oxygen saturation
- Categorical summary of observed vital signs and vital sign changes compared to Baseline (Visit 2 of Study MIV-711-201), by patient

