### 7.3 Secondary Endpoints (Study Population B)

These are the same as the primary endpoints for Study Population A (see Section 7.1).

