## 7.13 Adverse Events

### 7.13.1 Definitions of Adverse Events (AEs)

An AE is any untoward medical occurrence that occurs in a patient or clinical investigation patient administered a pharmaceutical product, and which does not necessarily have to have a causal relationship with this treatment. An AE can therefore be any unfavourable and unintended sign (including abnormal laboratory finding), symptom, or disease temporally associated with the use of an investigational product, whether or not considered related to the product.

All AEs, including undercurrent illnesses, occurring during the study will be documented in the eCRF system. Concomitant illnesses, which existed before entry into the study, will not be considered AEs unless they worsen during the treatment period. All AEs, regardless of the source of identification (e.g., physical examination, laboratory assessment, ECG, reported by patient), must be documented. Worsening of the underlying disease is not considered an AE and should be reported as such only if deemed by the Investigator to be beyond the expected progression for OA.

Pre-existing conditions will be recorded in the eCRF system on the Medical History page.

A treatment-emergent AE (TEAE) will be defined as an AE that begins or that worsens in severity after at least one dose of IMP has been administered.

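### Clinically significant knee worsening within expected OA progression is an adverse event under Protocol 7.5 but not under Protocol 7.13.1, and neither document says which rule governs

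*Protocol*

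**What the plan says.** Protocol 7.5 (Physical Examination) states: "A standard clinical examination of both knees will be undertaken at all visits". The next sentence is the recording rule: "Any clinically significant changes from Visit 2 (Enrolment) should be recorded as AEs". It makes no exception for OA and does not point to the AE definitions.

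Protocol 7.13.1 (Definitions of Adverse Events) sets a different rule: "Worsening of the underlying disease is not considered an AE". Such worsening is to be reported as an AE "only if deemed by the Investigator to be beyond the expected progression for OA". The same section covers findings from examination: "All AEs, regardless of the source of identification (e.g., physical examination, laboratory assessment, ECG, reported by patient), must be documented".

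The endpoint fed by these rules is "Incidence and severity of AEs", the first of six safety endpoints listed for Population A in Protocol 7.1. Protocol 7.3 carries the list over to Population B as secondary endpoints: "These are the same as the primary endpoints for Study Population A".

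SAP 9.1 defines a TEAE by onset or worsening after dosing and adds nothing about knee or OA findings. SAP 9.5 has abnormal examination findings listed only. For laboratory values, SAP 9.2.1 does say that clinically significant results go into the AE listings. It has no matching sentence for the knee.

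**The concern.** All patients in the study have knee OA, and their knees are examined repeatedly. A worse knee on examination is a foreseeable finding, and the protocol gives two instructions for it that lead to opposite entries in the eCRF. A site that follows 7.5 records an AE. A site that follows 7.13.1, and regards the change as ordinary progression, does not.

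The SAP counts AEs as they were recorded, so a difference in recording passes straight into the TEAE tables. The study has one arm, so there is no concurrent control group in which the same recording habit would operate. The committee's safety reviews also rest on AE summaries (Protocol 8.3 and 9.6; SAP 3.6). At stake is whether reported AE incidence in MIV-711-202 reflects patients' experience alone or partly how each site read the protocol.

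**Working it through.** The plan states no figure on this point, so there is nothing to reproduce. The check is to apply both rules to each kind of knee change found after Visit 2 of MIV-711-202.

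| Knee change after Visit 2 | Under 7.5 | Under 7.13.1 |
|---|---|---|
| Due to OA, within expected progression, not clinically significant | not an AE | not an AE |
| Clinically significant, not due to OA (an injury, for example) | AE | AE |
| Clinically significant, due to OA, beyond expected progression | AE | AE |
| Clinically significant, due to OA, within expected progression | **AE** | **not an AE** |

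The rules agree in three rows and conflict in the fourth. Three further checks:

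1. *Do both rules reach the same finding?* Yes. 7.13.1 names physical examination as a source of AEs. The 7.5 sentence may be meant for the whole physical examination or only for the knees, but it covers the knees on either reading.
2. *Is there a tie-breaker?* No. Neither document says which section governs. Neither defines clinical significance for a knee finding or says what progression is expected.
3. *Does the SAP settle it?* No. TEAEs are counted as recorded (SAP 9.1). A knee finding not recorded as an AE appears in a listing (SAP 9.5) and in no safety summary table.

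**Scale.** The one usable input is the expected total of 50 to 80 patients, Populations A and B together (Protocol 5.4). If k patients have such a finding as their only AE, overall incidence changes by k/N. For k = 1:

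- N = 80: 1/80 = 1.25 percentage points
- N = 50: 1/50 = 2.0 percentage points

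The documents do not give the split between the populations. Population A is smaller than the total, so one patient counts for more than this in its column. A patient who also has another AE does not move overall incidence, but does move the count for the knee or musculoskeletal term unless that term is already recorded for the patient.

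**The case against.** The strongest reply is that the sections can be read together. 7.13.1 is the formal definition, it mentions physical examination, and its OA exception follows soon after. 7.5 turns on clinical significance, which it leaves undefined and which is the investigator's judgement for ECGs (Protocol 7.7) and laboratory values (Protocol 10.6). The same investigator could regard expected OA progression as not clinically significant, or treat the OA exception as the special rule. That reading is available, and no divergence between sites has been shown. But the text does not require it. The 7.5 sentence stands directly after the knee examination, so it is no less specific, and it has no cross-reference.

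Other parts of the reply stand and limit the point:

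- A reader might infer that a signal of joint worsening could vanish from the study. The documents do not support that. Examination findings by patient are themselves a primary safety endpoint (Protocol 7.1), and Listing 16.2.8.11 shows abnormal findings with their clinical significance. Knee pain, function and MRI structure are also analysed by group (SAP 8.1 to 8.3). What can be lost is the event's place in the AE tables.
- A reader might infer that the primary result is hit hardest because Population B was selected for worsening symptoms. Primary presentations use Population A (Protocol 9.5.1), which was selected for the absence of significant deterioration. The selection argument bears only on the secondary objective.
- The primary period is 26+26 weeks. AEs of the first 26 weeks were recorded under the MIV-711-201 protocol, which is not among these documents. The conflict is shown only for the MIV-711-202 part.
- Requiring every such change to be recorded as an AE would override an exclusion that the protocol states on purpose. The defect calls for one rule, not for a particular one.

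**Conclusion.** The plan is wrong as written on a narrow point. For clinically significant, OA-related knee changes within expected progression, two stated rules give opposite answers and nothing ranks them. This is a conflict, not missing detail. It can make AE recording differ between sites and so affects AE incidence, one of six listed primary safety endpoints in Population A and a secondary endpoint in Population B.

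The size is unknown because the documents give no rate. The only scale that they support is 1.25 to 2.0 points of overall incidence per patient whose sole AE is such a finding, assuming the planned 50 to 80 patients. The study is descriptive and not powered for confirmatory analysis (Protocol 9.2.1), so no decision threshold depends on the shift.

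Two larger figures are tempting. If a share q of patients had such a finding, and a share p had some other AE independently, overall incidence would rise by q(1 − p). With q from 5% to 20% and p from 40% to 60%, that runs from 0.05 × 0.40 = 2 points to 0.20 × 0.60 = 12 points. The arithmetic is right, but every input is assumed, so it is not an estimate for this trial. Nor would knee AEs be close to zero under 7.13.1: injuries and worsening beyond expectation count under both sections.

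**What to change.** 1. **Protocol.** Reconcile 7.5 and 7.13.1 so that one stated rule governs OA-related knee findings, with a cross-reference in each section.
2. **SAP 9.1.** Show overall TEAE incidence and the musculoskeletal class with and without knee/OA events, by group. Identify the events by a pre-specified list of preferred terms, plus clinically significant knee findings in Listing 16.2.8.11 where these were entered there. The listing matters because a term search cannot find an event that a site never recorded as an AE.
3. **Study report.** State that the recording rule was ambiguous.

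Conduct was planned to end in August 2017 (Protocol 10.11) and the SAP is dated 16 January 2018, so the wording change may come too late to alter recording. Items 2 and 3 remain feasible.

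The cost is a clause in the protocol, a term list and a few extra table rows. Reported AE incidence may be slightly higher in the version that includes the knee/OA events. The two versions show how far the safety result depends on how sites read the protocol, to the extent that knee findings were entered in the listing.

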## 7.6 Vital Signs

Vital signs (body temperature, heart rate, blood pressure, oxygen saturation) will be performed at all clinic visits prior to IMP dosing.

Blood pressure and heart rate measurements will be performed after the patient has been resting in a supine position for at least 5 minutes.

Weight will be measured at Visit 1 (Screening).

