## **2.2 Pharmacokinetic, Pharmacodynamic and Safety results from MIV-711 First Time in Man Study and Blinded Safety and Tolerability Summary from MIV-711-201**

A First Time in Man (FTIM) study with MIV-711 has been conducted in male and female healthy volunteers including single doses up to 600 mg, multiple doses up to 200 mg once-daily (q.d.) for 7 days and in healthy post-menopausal female volunteers at multiple doses of 100 mg q.d. for 28 days. The single dose part enrolled 18 males and 9 females with an age range of 19-64 years. The multiple dose parts enrolled 15 males and 24 females with an age range of 18-65 years. The primary objective was to determine the safety and tolerability of ascending single and multiple oral doses of MIV-711 in healthy volunteers.

MIV-711 was rapidly absorbed after oral administration with peak concentrations typically occurring 1 hour after administration. A high fat meal prolonged the absorption but had no apparent effect on systemic exposure measured by area under the concentration-time curve from zero to infinity ( $AUC_{\infty}$ ) of MIV-711. The mean terminal half-life was 3.3 to 5.2 hours over the 20 to 200 mg dose range. Observed maximum measured plasma concentration ( $C_{max}$ ) and  $AUC_{\infty}$  increased in close proportion to dose over the single dose range 100-600 mg. Following multiple oral administration of 50 to 200 mg q.d. for 7 days or 100 mg q.d. for 28 days, no accumulation of MIV-711 was observed. MIV-711 was indicated to be extensively metabolised with less than 1% excreted unchanged by the kidney. No gender differences in dose normalised  $C_{max}$  or  $AUC_{\infty}$  for MIV-711 were observed. Further details on MIV-711 metabolism can be found in the IB.

A dose-dependent reduction in the biomarkers serum CTX-I and urinary CTX-II was observed after single and multiple doses of MIV-711, by down to 55 and 72% from Baseline respectively at multiple dosing (for further details see Section 2.4, Section 2.5 and the IB).

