### 6.2 Administration

Patients will receive q.d. 200 mg oral dose of MIV-711 for 26 weeks in addition to their current medication.

The IMP should be taken q.d. in the morning approximately 24 hours apart and swallowed whole together with a glass of water (approximately 200 ml) before breakfast; breakfast can be taken approximately one hour later. The first dose in Study MIV-711-202 is administered at the site during Visit 2 (Enrolment). All patients must stay at the site 2 hours after administration of the first dose.

IMP should be dispensed during the Visits 2 and 4 and returned by the patients for drug accountability at Visit 4 and Visit 5.

On days when the patient is visiting the site the IMP must be taken at the site under fasting conditions (and not at home) and the time of the intake must be recorded in the source documents.

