4.4.4 Vital Signs

Vital signs (body temperature, heart rate, blood pressure, oxygen saturation) will be performed at all clinic visits prior to IMP dosing: Visit 1 (screening), Visit 2 (Week 1), Visit 3 (Week 4), Visit 4 (Week 14), Visit 5 (Week 26), Visit 6 (Week 30), safety follow up. All assessments will be collected in the supine position.

Weight will be measured at visit 1 (screening).

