9.3 Vital Signs

The observed data for blood pressure (systolic and diastolic), heart rate (pulse), pulse oximetry, and body temperature will be listed by patient, and time point. Change from baseline values for blood pressure (systolic and diastolic), and heart rate (pulse) will be derived and listed. The overall qualitative assessment for vital signs will be listed.

For systolic and diastolic blood pressure and heart rate, the observed values and change from baseline data will be summarized by group and time point. Table summaries will include descriptive statistics showing the number of observations (n), mean, SD, median, minimum, and maximum value.

Figures of the observed mean response will be used to visualize blood pressure and heart rate response by time point. The two study groups will be shown in the same figure.

PAREXEL International Statistical Analysis Plan

Medivir
Protocol: MIV-711-202

Final 1.0
16 January 2018

9.4 12-Lead Safety ECG

Observed quantitative results for RR, PR, QRS, QT, QTcB (corrected QT according to Bazett), QTcF (corrected QT according to Fridericia) and heart rate will be listed for each patient. Change from baseline for QT, QTcB, QTcF will be derived and listed.

The overall qualitative ECG assessment Abnormal NCS, Abnormal CS, and any comments will be listed for each patient.

For QT, QTcB, QTcF the observed and change from baseline data will be summarized by study group and time point. Summaries will include tables of descriptive statistics showing the number of observations (n), mean, SD, median, minimum, and maximum value.

Figures of the observed mean response will be used to visualize QTcB and QTcF response by time point. The two study groups will be shown in the same figure.

The number and percentage of patients having observed QT, QTcB, QTcF values that satisfy the following conditions will be summarized by time point and study group:

- ≤ 450 msec
- $450 < \text{to} \leq 480$ msec
- $480 < \text{to} \leq 500$ msec
- > 500 msec

The number and percentage of patients having change from baseline QT, QTcB, QTcF values that satisfy the following conditions will be presented by time point and study group:

- ≤ 0 msec
- $> 0 \text{ to} \leq 30$ msec
- $> 30 \text{ to} \leq 60$ msec
- > 60 msec

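### Study 202 takes blood pressure, oxygen saturation and temperature only before dosing, at about 1–5% of peak drug level on treatment, and near-peak ECG heart rate is listed but not summarised

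*Protocol*

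**What the plan says.** Protocol 7.6 fixes the timing: "Vital signs (body temperature, heart rate, blood pressure, oxygen saturation) will be performed at all clinic visits prior to IMP dosing". SAP 4.4.4 says the same for Visits 1 to 6 ("will be performed at all clinic visits prior to IMP dosing"). Neither the visit lists in Protocol 8.1 nor Table 2 adds a post-dose set.

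Vital signs are primary. Of the six safety endpoints in Protocol 7.1, two concern them: a categorical summary by patient, and "Mean change from Baseline (Visit 2 of Study MIV-711-201) in vital signs (blood pressure, heart rate, temperature) and oxygen saturation".

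On exposure, Protocol 6.2 says "The IMP should be taken q.d. in the morning approximately 24 hours apart", with the capsule taken at the site on visit days. Protocol 2.2 reports "MIV-711 was rapidly absorbed after oral administration with peak concentrations typically occurring 1 hour after administration", adds that "The mean terminal half-life was 3.3 to 5.2 hours over the 20 to 200 mg dose range", and found no accumulation.

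ECGs follow a different timetable. Protocol 7.7 asks for them pre-dose and at 0.5, 1 and 2 h after the Visit 2 dose, and 30 minutes (±10) after dosing on other dosing days. SAP 9.4 lists heart rate from these tracings for each patient. It carries only the QT variables further ("Change from baseline for QT, QTcB, QTcF will be derived and listed"), and its summary tables cover QT, QTcB and QTcF alone. The heart rate that is tabulated (SAP 9.3, Table 14.3.3) comes from the pre-dose vital signs. SAP 9.3 lists saturation and temperature without summarising them.

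**The concern.** The drug is short-lived relative to its dosing interval, and the vital signs are taken at the end of that interval. The analysis compares them with a baseline taken before any 200 mg dose. An effect on blood pressure or saturation that follows plasma concentration and fades within hours would leave little trace in these readings. A flat table could then be read as showing that the drug has no effect on vital signs, when it shows only that no effect lasts to the next dose. The data that could address heart rate near peak are collected but do not reach a summary table.

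**Working it through.** The documents state no trough-to-peak fraction, so there is no planned figure to reproduce.

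**Inputs.** Peak at 1 h, half-life 3.3–5.2 h and no accumulation (Protocol 2.2); dosing interval 24 h (6.2); mean steady-state peak at 200 mg 0.58 µM (6.6.2); AUC over 24 h 2.4 µM·h (2.5).

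**Step 1: simple decay from the peak.** Fraction of peak at 24 h = 2^(−(24−1)/t½).
- t½ = 3.3 h: 2^(−23/3.3) = 0.8%, or 0.005 µM
- t½ = 5.2 h: 2^(−23/5.2) = 4.7%, or 0.027 µM

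Varying the decay time from 22 to 25 h widens the range to 0.5–5.3%.

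**Step 2: one-compartment oral model.** C(t) ∝ exp(−ke·t) − exp(−ka·t), with ke = ln2/t½ and ka solved from ln(ka/ke)/(ka−ke) = 1 h.

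| t½ (h) | ka (per h) | C(24)/Cmax | C(0.5)/Cmax |
|---|---|---|---|
| 3.3 | 2.80 | 0.9% | 87% |
| 4.0 | 3.04 | 2.0% | 88% |
| 5.2 | 3.36 | 4.9% | 89% |

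If the peak came at 2 h, the trough would be 1.3–6.0%.

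**Step 3: consistency checks.**
- The accumulation ratio 1/(1 − 2^(−24/t½)) is 1.007 to 1.043, which agrees with the reported absence of accumulation.
- Take a linear rise to 0.58 µM at 1 h, then a single exponential. The tail area is 2.4 − 0.5×0.58×1 = 2.11, so k = 0.58/2.11 = 0.275 per h and t½ is about 2.5 h. The trough is then about 0.2%. On this check, 1–5% does not make the trough look too low.

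**Step 4: apply to the visits.**

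| 202 visit | Drug state at vital signs | ECG after dosing |
|---|---|---|
| 2 | Group A 10±5 days off drug; Group B not yet exposed | 0.5, 1, 2 h |
| 3, 4, 5 | about 24 h after a capsule, roughly 1–5% of peak | 30 min |
| 6 | about 4 weeks off drug | no dose given |

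Visit 1 is also a trough for Group A when it is held with 201 Visit 8 and the readings precede that day's capsule.

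The 30-minute ECG sits at 87–89% of modelled peak (72–96% across the ±10 minute window). The 1 h ECG is at the stated peak time, and the 2 h ECG is at 2^(−1/t½) = 81–88% by simple decay. The ECGs therefore sample near-peak exposure and the vital signs do not.

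**The case against.** The case on the other side is substantial.

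- **Heart rate is observed near peak.** A reader might infer that a peak effect on pulse cannot be detected. The documents do not support that: post-dose ECG heart rate is recorded and appears by timepoint in Listing 16.2.8.8. What is missing is a summary.
- **The atrial fibrillation case does not argue for more blood pressure readings.** Protocol 2.2 describes one asymptomatic case in the first-in-man study, found on a scheduled ECG. Post-dose ECGs reviewed by the investigator are the tool for that, and ECG abnormalities are a primary endpoint in their own right.
- **Plasma level is not effect.** Rested, pre-dose readings are a standardised way to look for sustained change, which is what a long-term extension is about. The biomarkers are also sampled pre-dose, so the design expects some drug effects to be measurable at trough.
- **Acute effects have some cover.** The first-in-man study went to 600 mg single doses and to 200 mg daily for 7 days without clinically meaningful vital-sign effects. In 202, symptomatic events would be reported as adverse events, and patients stay on site for 2 h after the first dose.
- **Added readings would be hard to interpret.** Without a concurrent control, same-day change cannot separate drug from rest, fasting or time of day.

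These arguments narrow the point without removing it. The first-in-man summary does not say when its vital signs were taken. Adverse event reporting would not pick up a silent change in blood pressure or saturation. The listed ECG heart rates still need a table before anyone can judge a group-level shift.

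**Conclusion.** The point holds in a limited form. In Study 202, blood pressure, oxygen saturation and temperature are never scheduled near peak. On treatment at Visits 3–5 they are read at about 1–5% of peak concentration, so a no-change result speaks only to effects that last to trough. Near-peak heart rate exists in the data and is under-used.

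Two further inferences should be resisted. Not every 202 reading is a 24 h trough, because patients are off drug at Visits 2 and 6. The limitation also cannot be extended to the full 52 weeks: Group A's first 26 weeks come from Study 201, and the 201 schedule in SAP 4.1 gives timing relative to dose for ECGs but not for vital signs.

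The 1–5% rests on first-order elimination, the half-life range reported across 20–200 mg in healthy volunteers, and capsules taken about 24 h apart. It describes exposure and makes no claim that a peak effect exists.

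**What to change.** **SAP change, no new data.** Add heart rate to SAP 9.4 and Table 14.3.4.1. Give observed values and change from the pre-dose ECG of the first 200 mg day (201 Visit 2 for Group A, 202 Visit 2 for Group B), by nominal post-dose time: 0.5, 1 and 2 h at Visit 2 and 30 minutes at Visits 3–5. Show Group B's serial ECG heart rate from 201 Visit 2 alongside. That was a placebo day with the same timepoints (SAP 4.1, note C), so it gives a within-patient reference for the effect of the visit itself. State the baseline in the footnote: Table 14.3.4.1 uses 202 Visit 2 for Group B, whereas Table 14.3.4.3 and Listing 16.2.8.9 use 201 Visit 8, where the ECG is scheduled post-dose. The cost is SAP wording and one more parameter in an existing table.

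**Report wording.** Say that the 202 blood pressure and saturation results describe pre-dose conditions. This costs one sentence.

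**Optional, if visits remain.** Repeat blood pressure and saturation at the existing post-dose ECG slot and tabulate them apart from the pre-dose values. This adds a few minutes per visit and carries the no-control limitation noted above. Protocol 10.11 planned the study to end in August 2017 and the SAP is dated January 2018, so the first two changes may be the only ones still available.
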